6.5.3 Sensitivity Analysis

In order to assess the robustness of the primary efficacy results derived from the mITT population, a sensitivity analysis will be conducted using the PP population with the above-mentioned mixed effect model for the primary efficacy endpoint.

6.6 Safety Analyses

The safety and tolerability of AG-86893 will be determined by incidence and severity of treatment emergent AEs, abnormal changes in vital signs, clinical and laboratory results, BCVA, IOP, eye examinations, biomicroscopy and ophthalmoscopy examinations.

All safety analysis will be based on the Safety population.

6.6.1 Adverse Events

All AEs reported during the study period will be recorded and coded using MedDRA terminology (MedDRA V21.0 at time of SAP publication, or the current version when superseded). An AE will be considered as treatment-emergent adverse event (TEAE) if it has an onset during the treatment period. A pre-existing event that worsens after the first dose date and within 3 days after the last dose date is considered a treatment emergent event.

The incidence of all TEAEs will be summarized using system organ class and preferred term by treatment group and overall. Adverse events will also be presented by relationship and severity. Further, serious adverse events and those events leading to discontinuation will also be presented.

Participants may have more than one AE per system organ class and preferred term. At each level of participant summarization, a participant will be counted once if they reported 1 or more events and will be reported with the highest severity. In cases where severity or relationship is missing, the most conservative approach will be taken (i.e. highest severity and assumed to be related).

The following overall summary will be presented by treatment and overall:

- Total number and percent of participants with
 - All AEs
 - Mild AEs
 - Moderate AEs
 - Severe AEs
 - Not related AE
 - Related AE
 - AE leading to death
 - AE leading to treatment discontinuation

- Total number and percent of participants with SAE
 - Mild SAE
 - Moderate SAE
 - Severe SAE
 - Not related SAE
 - Related SAE
 - SAE leading to Death
 - SAE leading to treatment discontinuation

The following summary tables of AEs will be presented by treatment and overall:

- Total number and percent of participants with AEs
 - By system organ and preferred term
 - By frequency for SAEs

- Total number and percent of participants treatment-related AEs
 - By preferred term and severity

The number and percent of participants with significant vital sign and laboratory findings during study will be summarized by group and overall.

The number and percent of participants with the following special interest events will be summarized by group and overall.

- Abnormal liver function (as defined in section 4.7.1)
- Ocular events

Participant level listing will be provided with related information that include AE onset/resolution date, study days, duration, preferred terms, relationship to study eye drop, action taken, outcome, and sorted by treatment, subject ID and onset date.

6.6.2 Vital Sign, Laboratory and Ocular Findings

The following assessments will be summarized by group and overall for each study visit.

- Tear film break-up time
- Lissamine green conjunctival staining
- Intraocular pressure
- Best-corrected visual acuity
- Electrocardiogram

The number and percent of participants with abnormal findings at each visit for the following assessments will be summarized by group and overall.

- Slit-lamp biomicroscopy examination
- Dilated fundus examination

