### Day 84 (Week 12)

#### Off study drug/Exit

- Concomitant medications, concurrent procedures, participant questionnaire, physical characteristics, vital signs
- Pregnancy test, ECG
- Laboratory tests (hematology with differentials, serum chemistry, urinalysis)
- Ocular assessments (BCVA, IOP, biomicroscopy, TFBUT [optional], lissamine green conjunctival staining [optional], ophthalmoscopy)
- AE evaluation

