### 1.3 SCHEDULE OF ACTIVITIES

Procedures	Screening Day -14 to -2 (SCR)	Enrollment/ Baseline Visit 1, Day 1 (V1D1)	Study Visit 2 Day 7 ±3 days (V2D7) ☎*	Study Visit 3 Day 28 ±3 days (V3D28)	Study Visit 4 Day 56 ±5 days (V4D56)	Final Study Visit 5 Day 84 ±5 days (V5D84)
Informed consent	X					
Demographics	X					
Medical, smoking, alcohol and drug history a	X					
Concomitant medication	X	X	X	X	X	X
Compliance assessment b			X*	X		
Concurrent procedures	X	X	X	X	X	X
Participant questionnaire c		X c	X	X c	X	X
Physical characteristics k	X			X		X
Vital signs d	X	X	X*	X	X	X
Hematology	X		X*	X		X
Serum chemistry	X		X*	X		X
Urinalysis	X		X*	X		X
Urine pregnancy test e	X	X		X		X
ECG (12-lead)	X	X		X		X
BCVA	OU	OU	OU*	OU	OU	OU
Ocular photography f	OU	SE	SE*	SE	SE	
AS-OCT g		SE	SE*	SE	SE	
IOP	OU	OU	OU*	OU	OU	OU
Biomicroscopy	OU	OU	OU*	OU	OU	OU
TFBUT		OU		OU	OU	OU h
Lissamine green staining		OU		OU	OU	OU h
Ophthalmoscopy	OU	OU		OU		OU
Plasma drug monitoring i		X		X	X i	
Randomization		X				
Study drug j		X		X		
AE review and evaluation		X l	X	X	X	X

\* Study Visit 2 (V2D7) is a phone call follow-up but may be conducted as an optional in-clinic visit at the discretion of the Principal Investigator. Asterisked assessments will only be conducted during in-clinic visit

- a) Medical history will include history of sun exposure
- b) On Day 7, study drug bottle will be weighed and returned if the visit is conducted in-clinic. If the visit is via phone, participants will be verbally instructed to maintain compliance and use the provided diary. On Day 28, study drug will be collected after administration of last dose and study drug bottles will be weighed
- c) Participant questionnaire will be administered prior to study drug administration at Visits 1 & 28
- d) Blood pressure, pulse, temperature, and breathing rate
- e) Females of childbearing potential only
- f) Ocular photography will be submitted to central reading center for assessment of conjunctival hyperemia, pterygium vascularity and pterygium vessel length
- g) At selected sites, AS-OCT imaging will be performed and submitted to central reading center for assessment of pterygium volume
- h) Test is optional at Day 84; to be performed if test shows abnormal findings at Day 56

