### 9.3 POPULATIONS FOR ANALYSES

Three analysis populations will be defined and used in the statistical analyses: (1) a safety population, (2) a modified intent-to-treat (mITT) population, and (3) a per-protocol (PP) population.

Safety analyses will evaluate all randomized participants who received at least 1 dose of study drug and attended a post-baseline visit. Results will be presented based on the treatment received.

The primary statistical analyses will evaluate the mITT population, defined as all randomized participants who received at least 1 dose of study drug and had conjunctival hyperemia evaluated at both the Day 1 and Day 28 visits. Results will be presented based on the treatment assigned during randomization.

As a sensitivity analysis, the primary efficacy endpoint of conjunctival hyperemia will also be evaluated in the PP population of participants, who had no major protocol violations. Nominal data will be analyzed using the Pearson chi-square test or Fisher exact test. Conjunctival hyperemia, pterygium vascularity, BCVA, ophthalmoscopy, AS-OCT, and IOP data will be analyzed using analysis of variance models with dose strength as main effects. The analysis will be based on observed data. Missing values will not be imputed.

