3.1.4 Safety and Other Measures

a) Vital Sign and Laboratory Findings

Vital signs as listed below will be performed at all visits.

- Temperature ((Celsius)
- Respiratory Rate
- Systolic Blood Pressure
- Diastolic Blood Pressure
- Heart Rate
- Height (cm)
- Weight (kg)
- Body Mass Index (kg/m²)

Blood and urine samples will be collected for lab tests at Screening, Day 28, Day 84 or Early Discontinuation, and Unscheduled visits for the following tests:

- Urinalysis
- Hematology
- Serum chemistry

b) Physical Characteristics

c) Pregnancy Testing (for child-bearing participants)

d) Electrocardiogram (ECG) Findings

ECG will be performed at Screening, Day 1, Day 28, Day 84 or Early Discontinuation, and Unscheduled visits. Findings will be recorded as Abnormal or Normal.

e) Best-corrected Visual Acuity (BCVA)

BCVA using the Early Treatment Diabetic Retinopathy Study (ETDRS) visual acuity protocol will be assessed for both eyes at all scheduled visits. The number of letters read correctly will be recorded for both eyes.

f) Intraocular Pressure (IOP)

IOP (mmHg) will be measured using Goldmann applanation tonometer for both eyes at all scheduled visits.

g) Tear Film Break-up Time (TFBUT)

TFBUT (seconds) will be performed for the study eye first, then the other eye at Day 1, Day 28, Day 56, Day 84 (only if abnormal findings on Day 56) and Early Discontinuation visits.

h) Lissamine Green Conjunctival Staining

Conjunctival staining will be performed for the study eye first, then the other eye at Day 1, Day 28, Day 56, Day 84 (only if abnormal findings on Day 56) and Early Discontinuation visits using the following grading:

- 0 = None
- 1 = Mild
- 2 = Moderate
- 3 = Severe.

i) Biomicroscopy

Slit-lamp biomicroscopy examination for both eyes will be performed at all visits for following measurements:

- Eyelids (Abnormal, Normal. If Abnormal, specify)
- Conjunctiva (0 = None, 0.5 = Trace, 1 = Mild, 2 = Moderate, and 3 = Severe)
- Cornea (0 = None, 0.5 = Trace, 1 = Mild, 2 = Moderate, and 3 = Severe)
- Iris (0 = None, 0.5 = Trace, 1 = Mild, 2 = Moderate, and 3 = Severe)
- Lens Status (Clear, Opacity, Pseudophakic, Aphakic)
If Opacity:
 - Nuclear Cataract Grade (: <1, 1, 1.5, 2, 2.5, 3, >3)
 - Posterior Subcapsular Cataract Grade (: <1, 1, 1.5, 2, 2.5, 3, >3)
 - Cortical Cataract Grade (: <1, 1, 1.5, 2, 2.5, 3, >3)

j) Ophthalmoscopy Findings

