6 STATISTICAL METHODS

All data processing, summarization, and analyses will be performed using SAS® Version 9.4 or higher.

Unless otherwise specified, for continuous variables, descriptive statistics will include the number of participants/eyes (n), mean, standard deviation, median, minimum and maximum values. Categorical variables will be summarized using frequency and percentages.

Unless, otherwise stated, missing data will be handled as is, except when the aforementioned dates are required for calculations, the partial dates will have either '01' or 'Jan' imputed with an exception for dates related to AEs where the date closest to the last event (screening, first dose, last dose, etc.) should be used rather than arbitrary '01' of that month.

All efficacy data will be summarized by treatment group and time point using appropriate descriptive statistics. Summaries will be presented for both the mITT and PP populations. Due to the small number of participants that are expected to be enrolled at each center, all summaries and analyses will be performed using data pooled across centers.

Baseline results will be those recorded prior to dosing. In cases where more than one pre-dose observation has been recorded, the **last recording** will be identified as the baseline result.

Study days will be numbered relative to the date of the first dosing. The start of study (Day 1) will be defined as the date on which a participant takes the first dose of any study medication, as recorded on the CRF. Relative to study start, days will be numbered ...-2, -1, 1, 2, ... with Day - 1 being the day prior to the start of study medication (Pre-Dose).

Recorded data will be assigned to evaluation/assessment windows. If more than one clinical evaluation is made within a window for a particular visit, the record with the date closest to the targeted window will be used except for AEs where the **worst assessment** will be used.

Visit windows and analytical windows are defined as follow:

Visit	Targeted Window	Analytical Window
Pre-dose (Screening)	Day -14 to Day -1	Day -18 to Day -1
Visit 1 (First dosing date)	Day 1	Day 1
Visit 2 (optional)	Day 7 (± 3 day)	Day 2 to Day 16
Visit 3 (End of treatment visit)	Day 28 (± 3 days)	Day 17 to 3 days after the last dose and up to Day 42
Visit 4	Day 56 (± 5 days)	Day 43 to Day 70
Visit 5 (End of study visit)	Day 84 (± 5 days)	Day 71 to End of Study

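### SAP 6.6.2 summarises Day 84 tear break-up time and lissamine green by group, although only participants abnormal at Day 56 are due for retest, so stable or improving eyes can appear as late worsening

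*SAP*

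**What the plan says.** The schedule in protocol 1.3 puts TFBUT and lissamine green on both eyes of every participant at Days 1, 28 and 56. The Day 84 entries carry footnote h: "Test is optional at Day 84; to be performed if test shows abnormal findings at Day 56". The Day 84 block of the protocol schema likewise lists "TFBUT [optional], lissamine green conjunctival staining [optional], ophthalmoscopy", so ophthalmoscopy is unconditional there and the other two tests are not. SAP 3.1.4, items g and h, is stricter and gives the same limit for each test: "Day 84 (only if abnormal findings on Day 56".

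SAP 6.6.2 places both tests in a list introduced by "The following assessments will be summarized by group and overall for each study visit". It makes no exception for Day 84.

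Nothing fills the gap for participants who are not retested. SAP 6 states that "missing data will be handled as is", apart from rules on partial dates. Protocol 9.3 states "Missing values will not be imputed". SAP 6.2.3 does not map safety data from treatment-discontinuation exits to the next scheduled visit. For continuous variables, SAP 6 reports n, mean, SD, median, minimum and maximum. Neither document asks for a paired Day 56 to Day 84 summary, a fixed denominator or a note on the conditional testing.

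**The concern.** Three visits in the by-visit table describe the whole group. The fourth describes participants who had a poor result at the visit before it. That selection uses an outcome measured after randomization, which causes two problems.

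- **Across visits.** Day 84 is not comparable with Days 1, 28 and 56. Dropping the normal participants worsens the mean even if no eye has changed.
- **Across arms.** The retested subset can differ in size and make-up between arms, so a Day 84 comparison is no longer one of randomized groups.

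Both tests are named safety endpoints (protocol 3, SAP 4.7), and SAP 8 gives the final database lock the task of longer-term safety assessment. A reader asking whether an effect on the tear film or staining settles after dosing stops could take recovery for late deterioration.

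**Working it through.** The documents give no figure on this point, so there is nothing to reproduce. The check is arithmetic on the selection.

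**Inputs.** The testing rule comes from protocol 1.3 and SAP 3.1.4, the summary rule from SAP 6.6.2, and the absence of imputation from SAP 6 and protocol 9.3. About 20 evaluable participants per group comes from SAP 3.3. Shares abnormal, grades and seconds are assumptions, because the documents give no distribution.

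**Lissamine green.** Let p be the share abnormal at Day 56, m their mean grade, and d their mean improvement by Day 84. Everyone else is taken as grade 0, with one eye per participant and all abnormal participants retested.

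- Day 56 group mean = p × m
- Day 84 tabulated mean = m − d
- Apparent change = (1 − p) × m − d

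The table shows worsening whenever d < (1 − p) × m, which includes d = 0 (no eye changed) whenever p is below 1. If the others have mean grade r rather than 0, the threshold becomes (1 − p) × (m − r).

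Simple case: 6 of 20 at grade 1, of whom 3 resolve. Day 56 mean = 6/20 = 0.30. Day 84 mean = 3/6 = 0.50. With the untested kept at 0, the whole-group value would be 3/20 = 0.15. The threshold is 0.7 × 1 = 0.70 and d is 0.50, so the table shows worsening.

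Range over p, with 20 per group:

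| Abnormal at Day 56 | m | (1 − p) × m | Day 56 mean | Day 84, all stable | Day 84, half improve one grade (d = 0.50) |
|---|---|---|---|---|---|
| 2 (both grade 1) | 1.00 | 0.90 | 0.10 | 1.00 | 0.50 |
| 6 (four grade 1, two grade 2) | 1.33 | 0.93 | 0.40 | 1.33 | 0.83 |
| 10 (eight grade 1, two grade 2) | 1.20 | 0.60 | 0.60 | 1.20 | 0.70 |
| 14 (ten grade 1, four grade 2) | 1.29 | 0.39 | 0.90 | 1.29 | 0.79 |

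In the last column the true paired change is −0.50 in every row. The table shows a rise in the first three rows and a fall only in the fourth.

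**TFBUT.** Let a be the mean in seconds among those normal at Day 56, b the mean among the abnormal, and g the mean gain of the abnormal by Day 84. The Day 56 mean is (1 − p) × a + p × b and the Day 84 mean is b + g. The table shows a decline whenever g < (1 − p) × (a − b).

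- With a = 12, b = 6, g = 2 and 6 of 20 abnormal: Day 56 = (14 × 12 + 6 × 6)/20 = 10.2 s and Day 84 = 8.0 s. With the untested held at 12 s, the whole-group value is (14 × 12 + 6 × 8)/20 = 10.8 s.
- With a = 10, b = 4, g = 1 and 4, 6, 10 or 14 abnormal: Day 56 = 8.8, 8.2, 7.0 or 5.8 s, against 5.0 s at Day 84 each time. The gain needed before the decline disappears is 4.8, 4.2, 3.0 or 1.8 s.

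**Between arms.** Suppose one arm has 2 of 20 abnormal and another 10 of 20, all at grade 1 and stable. The Day 56 means are 2/20 = 0.10 and 10/20 = 0.50. Both arms show 1.00 at Day 84.

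**Fellow eyes.** Suppose 6 of 20 participants have one eye at grade 1, all fellow eyes are 0, both eyes are retested and pooled, and nothing changes. The mean goes from 6/40 = 0.15 to 6/12 = 0.50. The rise is 0.35, against 0.70 (0.30 to 1.00) with one eye per participant. The artefact is halved but still present.

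**The case against.** The case against giving this much weight has several parts.

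- **It is visible.** Each continuous summary carries n, line listings are planned, and the conditional rule is printed in SAP 3.1.4. A careful reader would see n drop at Day 84. This stands, but a visible n does not correct the group value. SAP Module II, which holds the table shells, is not among the documents, so whether a footnote exists there is unknown.
- **The size is not known.** It depends on p, and protocol 2.1 describes reduced tear film break-up in these patients, so p for TFBUT may be high. This stands: the artefact shrinks as p rises, and in the 14-of-20 lissamine case the table moves the right way.
- **The stakes are limited.** These are descriptive safety summaries in an exploratory Phase 2 study. This also stands.

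Four stronger readings are tempting, and the documents do not support them.

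- A reader might infer that Day 84 is the only look at recovery of the ocular surface. Biomicroscopy, adverse events and the questionnaire are scheduled for everyone at Day 84, and Day 56 is itself an off-drug visit with both tests in all participants.
- A reader might infer that the Day 84 data contain only abnormal eyes. Testing is on both eyes, the trigger is not stated per eye, and the protocol's word is optional, so some normal eyes may be included.
- A reader might infer that an arm imbalance would be hidden altogether. The full-sample Day 56 summary would still show it.
- A reader might infer that a between-arm Day 84 test is planned. SAP 6.5.2 says only that these tests might be explored with the primary approach, and names no visit for them.

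**Conclusion.** The point holds in a limited form. Followed as written, SAP 6.6.2 computes the Day 84 TFBUT and lissamine green summaries on a subset selected by the Day 56 outcome. Those values are not comparable with the full-sample visits or between arms, and they can suggest worsening when retested eyes are stable or better.

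The direction depends on the conditions derived above. The size cannot be fixed from the documents: it rests on an assumed share abnormal at Day 56, on the values among normal participants, and on how fellow eyes are handled. Neither document defines an abnormal result for either test, so retesting could also vary by site.

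The effect is confined to these two descriptive safety summaries, and the primary analysis is untouched. It is worth correcting because the rule as stated can mislead and the correction is cheap.

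**What to change.** In SAP 6.6.2, do not present Day 84 TFBUT and lissamine green as group summaries beside Days 1, 28 and 56. In SAP 6.5.2, exclude Day 84 from any between-arm model of these two tests. Report instead, by arm and in retested participants:

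- for TFBUT, the within-eye change from Day 56 to Day 84;
- for lissamine green, a within-eye shift table from Day 56 to Day 84;
- for both, the number retested, the number abnormal at Day 56 and the number tested at Day 56, with a footnote on the conditional testing.

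A count of persisting abnormality over all participants tested at Day 56 can be added. Those normal at Day 56 count as not persisting, and those abnormal but not retested are shown separately. For lissamine green this can use grade above 0. For TFBUT it must wait until the criterion that triggered retesting is recorded, since results are in seconds and no cut-off is stated.

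The cost is wording in the SAP and table shells, plus recording that criterion if the TFBUT count is wanted. No visit or test changes. The loss is a Day 84 group mean for these two tests.

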6.7 Pharmacokinetic Analyses (if data available)

Pharmacokinetic analysis, if applicable, will be based on the PK sub-population using a model-independent approach.

Drug plasma concentration data will be summarized for each dose by descriptive statistics using SAS®. AUC_{0-1h} will be estimated using linear trapezoidal method.

Individual and mean concentration at each time point, C_{max} , T_{max} , and AUC_{0-1h} , where applicable, will be presented by treatment group for Day 1 and Day 28. On Day 56 individual and mean \pm SD will be presented.

Individual and mean concentration-time curves will be presented for Day 1, and Day 28 to illustrate the dynamic change of plasma concentration from hour 0 to 1.

6.8 Patient Questionnaire

Severity and frequency scores of each symptoms of the study eye will be summarized by group for each visit.

7 CONVENTIONS AND ALGORITHMS

7.1 Decimal Points

All summary tables involving percentages will round the percentages off to 1 decimal place.

All summary tables involving descriptive statistics of continuous variables will round the mean and median to 1 decimal place more than the variable's standard form and round the standard deviation to 2 decimal places more than the variable's standard form. The standard form of a percent change variable is 0 decimal places.

7.2 Study Days

Study days will be computed for each visit and AE event.

Study Days = Date of Visit/Event - Date of First Dose + 1

Or, if the visit/event occurs prior to the Day 1

Study Days = Date of Visit/Event - Date of First Dose

Date of First Dose is the Day 1 Visit date.

Last Date in study is the Day 84 Visit or the last visit where the participant was seen by the investigator. If lost-to-follow-up, the last date of contact is the Last Date in study.

If a participant had contact with the site after the final visit (e.g. for AE follow up), the last visit date will be the Last Date in study, not the contact date.

Time in Study (Study duration) = Last Date in study – Date of First Dose + 1

Time in Study Treatment (Treatment duration) = Date of Last Dose – Date of First Dose + 1

7.3 Multiple Occurrence of Events

When summarizing AEs, potentially clinically important laboratory findings, potentially clinically important vital signs, and participants with multiple occurrences of an event will be counted only once in the summary. When AEs are summarized by severity, if the participant has multiple occurrences of the same AE, the most severe will be used for the summary.

When summarizing concomitant medications by drug class and by preferred term, if two medications are coded to the same preferred term, both will be counted for a participant.

